## **3 Disposition and Exit Status**

### **3.1 Screening Log Data**

The number of subjects who are screen failures versus those who are qualified will be tabulated. The characteristics (sex, race, and age) of the failed and qualified subjects will be summarized. In addition, reasons for failure will be tabulated by “inclusion” and “exclusion”. The screen failures will be listed by site.

### **3.2 Disposition and Exit Status**

A patient disposition and exit status table will be done for the all randomized subjects population. A cumulative frequency table showing patient disposition (enrolled, completed, and discontinued) in the study with sub-categorization by reason for premature discontinuation for each treatment group will be generated.

## 4

# **Demographics and Other Baseline Characteristics**

### **4.1**

## **Demographics**

The demographics will be summarized for the mITT population.

Age, race, sex will be summarized using frequency tabulations and/or summary statistics, both by treatment group and overall patients. Race will be classified as Caucasian and non-Caucasian (black, Asian, Hispanic, and other). In addition, race will be displayed as collected in the case report form (Caucasian, black, Asian, Hispanic, and other).

### **4.2**

## **Disease Characteristics**

For the mITT population, the MAS-B ankle score with knee extended and knee flexed at baseline, the history of disease including the type (hemiplegia and monoplegia), onset, duration, and previous botulinum toxin exposure status will be summarized by treatment group for the mITT population.

### **4.3**

## **Prior Medications**

Using the mITT population, the number and percent of patients who had taken prior medication (as defined in Section 2.3) will be presented by treatment group for the base preferred (drug) name according to the World Health Organization Drug Dictionary Enhanced (WHO DDE) with the same active ingredients by the primary system organ class (SOC) and preferred term of the MedDRA code.

### **4.4**

## **Concomitant Medications and Concurrent Procedures**

Concomitant medications (as defined in Section 2.3) will be presented by WHO DDE preferred drug name for each treatment group by the primary SOC and preferred term of the MedDRA code using the mITT population. Concurrent procedures will be listed for the mITT population.

### **4.5**

## **Medical History**

Data for medical history with onset dates prior to the initial informed consent form signed date will be tabulated and presented by the SOC and preferred term of MedDRA code for each treatment group using the mITT population.

## 4.6 Pre-treatment Adverse Events

Data for pre-treatment adverse events, adverse events with onset date in-between informed consent date and randomization/day 1 visit or medical history that worsened duration this period will be listed.

## 4.7 Pre-treatment Serious Adverse Events

All pre-treatment serious adverse events will be flagged in the pre-treatment adverse events listing.

## 5 Efficacy Analyses

The primary, secondary, and other efficacy endpoints are listed below. The efficacy analysis for US FDA is described in Section 10.

Primary efficacy endpoints:

- The average change from baseline in MAS-B ankle score with knee extended at weeks 4 and 6
- The average CGI by Physician at weeks 4 and 6 (co-primary efficacy endpoint for US FDA only)

Secondary efficacy endpoints:

- The average CGI by Physician at weeks 4 and 6 (for non-US FDA analyses)
- Goal Attainment Scale (GAS) by Physician
- Modified Tardieu Scale (MTS) of the ankle with knee extended and knee flexed

[REDACTED]

| [REDACTED]

| [REDACTED]

[REDACTED]

| [REDACTED]

## 5.1

### Collection and Derivation of Efficacy Assessments

The MAS-B will be used to evaluate spasticity of each of the injected muscle (gastrocnemius, soleus, tibialis posterior) based on rating the resistance encountered in a specific muscle by means of passively moving a limb through its range of motion at a specified velocity.

At day 1 and weeks 2, 4, 6, 8 and 12, the same investigator (when possible) will assess the patient's ankle muscle tone with knee extended and knee flexed . The investigator will extend the patient's ankle from a position of maximum possible plantar flexion to a maximum possible dorsiflexion. The resistance encountered to the passive stretch will be rated on the MAS-B as follows:

0 =	No increase in muscle tone
1 =	Slight increase in muscle tone, manifested by a catch and release, or by minimal resistance at the end of the range of motion when the affected part(s) is moved in flexion or extension
1+ =	Slight increase in muscle tone, manifested by a catch, followed by minimal resistance throughout the remainder (less than half) of the range of motion
2 =	More marked increase in muscle tone through most of the range of motion, but affected part(s) easily moved. There can be a catch, but movement should be stiff through most of range.
3 =	Considerable increase in muscle tone, passive movement difficult
4 =	Affected part(s) rigid in flexion or extension

The MAS-B scores of 0, 1, 1+, 2, 3, or 4 will be coded as a grade of 0, 1, 2, 3, 4, or 5, respectively. The MAS-B ankle score change from baseline to each post-randomization visit and the primary endpoint, average change from baseline at weeks 4 and 6, will be derived for each patient. Additionally, a responder status will be determined according to whether or not a patient has at least a 1-grade reduction from baseline in MAS-B ankle score.

The CGI by Physician will be measured at weeks 2, 4, 6, 8, and 12. There is no CGI assessment at baseline. The CGI is a 9-point scale from -4 (very marked worsening) to +4 (very marked improvement). Each assessment is evaluated relative to the patient's baseline status obtained at day 1. The secondary endpoint for CGI will be the average of weeks 4 and 6 scores. Additionally,

a responder status will be determined according to whether or not a patient has at least +1 score of CGI by Physician.

The secondary efficacy measures of average CGI by Physician at weeks 4 and 6, GAS, and MTS will also be collected at scheduled office visits according to the Schedule of Visits and Procedures in the protocol.

The GAS is used to measure functional goal attainment relative to the effect of the study intervention. The achievement of 2 functional goals, one active and one passive, preset at week -2 by the patient and family in consultation with the investigator and/or treating physical therapist relative to the lower limb impairment due to spasticity and confirmed at day 1, will be assessed at weeks 8 and 12 using a scale of -3 (worse than start) to +2 (improvements clearly exceed the defined therapeutic goal).

For MTS, the difference between slow and fast range of motion (R2-R1) and respective change from baseline to each post-treatment office visit will be derived. The MTS of the ankle will be used to determine the passive range of movement at different movement velocities, V1 (as slow as possible) and V3 (as fast as possible) with the relative difference between a slow and a fast velocity passive stretch determining the dynamic component of the muscle contracture for the joint. At each visit, the same investigator, when possible will measure two joint angles by goniometer: the R1 angle which is the “angle of catch” after a fast velocity (V3) stretch and the R2 angle defined as the passive joint range of movement following a slow velocity (V1) stretch. The R2 – R1 value indicates the level of dynamic contracture in the joint. The difference between slow (R2) and fast (R1) range of motion and respective change from baseline to each post-treatment office visit on the MTS will be derived.

[REDACTED]

[REDACTED]

[REDACTED]

## 5.2 Primary Efficacy Analyses

### 5.2.1 Primary Analyses of Primary Efficacy Variable

The primary efficacy analyses will be based on the mITT population. The primary analysis will be conducted for the average of change from baseline in MAS-B of the ankle plantar flexors with

knee extended at weeks 4 and 6. For the assessment of treatment groups in the primary endpoint, the statistical null hypothesis is that both BOTOX higher dose (8 U/kg) and lower dose (4 U/kg) have the same mean as placebo. The alternative hypothesis is that at least one study dose of BOTOX has a different mean than placebo. The hypothesis will be tested using Mixed Model Repeated Measures (MMRM) at significance level of 0.05. The primary variable will be summarized by treatment group. The differences of each BOTOX dose group and the placebo group will be used to test the null hypothesis. The analysis will include weeks 2, 4, 6, 8, 12 data. The model will include baseline MAS-B ankle score with knee extended as a covariate and factors of age group, treatment group, visit, treatment-by-visit interaction, study center and previous botulinum toxin exposure. Age group is represented by stratification categories ( $\leq 6$  years and  $> 6$  years). Baseline MAS-B ankle score with knee extended is a continuous variable included as a covariate. Pooled study center will be produced to ensure each contains at least 12 patients. Pooling method is described in Section 2.3.

A gate-keeping approach will be used to control the type I error rate for the primary endpoint. Specifically, 8 U/kg versus placebo will be tested first followed by the 4 U/kg versus placebo comparison, each at 2-sided 0.05 level. The 4 U/kg versus placebo comparison will only be performed if the test for 8 U/kg versus placebo is statistically significant.

The co-primary analyses for US FDA only is described in Section 10.

### **5.2.2                    Other Analyses of Primary Efficacy Variable**

For sensitivity analysis purposes to supplement the primary analyses, an analysis of covariance (ANCOVA) model using MI for missing values will be conducted. A summary of the percentage

of missing MAS-B ankle scores with knee extended by visit will also be provided. The ANCOVA will include baseline MAS-B ankle score with knee extended as a covariate and factors of age group, treatment group, study center and previous botulinum toxin exposure.

The ANCOVA model will be used to analyze each imputation dataset obtained from MI as described in Section 5.1. [REDACTED] will then be used to pool the analyses results across the imputation datasets and produce final parameter estimates. Additional sensitivity analyses for the MAS-B ankle score with knee extended changes from baseline at each assessment time point will also be performed using the same ANCOVA as specified above with observed data, and linear contrasts will be used to estimate the treatment differences between each study dose and placebo.

In addition, the frequency distribution of the grade changes from baseline on the MAS-B ankle score with knee extended, as well as the percentage of responders (with at least a 1-grade reduction in MAS-B), will be summarized by treatment group at each post-treatment office visit. A logistic regression analysis will also be performed on the responder status at each post-treatment visit with a covariate of baseline MAS-B ankle score with knee extended and factors of age group, treatment group, study center, and previous botulinum toxin exposure, if applicable. The additional analyses will be conducted using observed cases unless stated otherwise.

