7.5 Sample Size Calculation

Approximately 412 patients will be enrolled to ensure that at least 351 patients (117 per treatment group) will complete the study.

Using a 2-sample t-test, a significance level of 0.05, and the assumptions in Table 4, the power for MAS-B change from baseline is 94% (PASS, Hintze, 2008). The calculation is based on assumptions for 8 U/kg group and placebo group. Since there are 2 co-primary endpoints for the US FDA analysis, for 8 U/kg group the power for CGI by Physician is calculated to be 97%, and the overall power for the US FDA co-primary endpoints will be at least 91%. The assumptions for MAS-B were based on results of completed Studies BTX108509 and BTX108512; the estimates for CGI were based on results of completed Study 191622-021.

Table 4 **Sample Size Assumptions and Power Calculations**

Endpoint	Average of Week 4 and 6 for 8 U/kg group	Average of Week 4 and 6 for Placebo group	Standard Deviation	Power
MAS-B Change from Baseline	-0.8	-0.45	0.75	94%
CGI by Physician (Co-primary for US FDA Analysis)	1.2	0.6	1.2	97%
Overall Endpoints				91%

CGI = Clinical Global Impression of Overall Change; MAS-B = Modified Ashworth Scale – Bohannon; US FDA = United States Food and Drug Administration

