- Data from unscheduled visits or re-test visits will be treated the same way as scheduled visits, ie, the dates of such visits will be used in the categorization of visit window. The algorithm handling multiple visits within a visit window will also be applied to unscheduled visits and re-test visits.
- For the primary and secondary efficacy analyses where study center is a factor in the analysis model, centers that recruited only a few patients will be pooled together. The following algorithm for pooling study centers will be used:
  - A. Pooling of study centers will by country.
  - B. Within each country, the following will be conducted:

1. Study centers will be ranked in descending order of the total number of patients enrolled.
2. Any center with at least 12 patients will stand on its own.
3. The first center with fewer than 12 patients will be combined with the next center until the total number in the pooled center reaches or exceeds 12 patients.
4. The algorithm of combining centers will continue down the list as described above.
5. If the last pooled center still has less than 12 patients, the last pooled center will be combined with the previous pooled center.

C. If there are less than 12 subjects enrolled in a country, the country will be pooled to the smallest center in the same region (alphabetical order if there is a tie). The regions include Asia-Pacific, Europe, and North America. For example, if Canada enrolled less than 12 patients, Canada will be pooled with a smallest center in the United States.

- The mean change from baseline for a given treatment group will be calculated by taking the sum of all individual changes from baseline divided by the number of patients with observations in that treatment group. As a consequence, patients without the particular follow-up data will not be taken into account, except if there is a missing value replacement method used.

|

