### **5.3.1 CGI by Physician**

CGI by Physician will be rated at study weeks 2, 4, 6, 8, and 12. Descriptive statistics will be presented by treatment group at each assessment timepoint and for the average of weeks 4 and 6. CGI by Physician will be summarized and analyzed by MMRM, as well as ANCOVA at each assessment timepoint using observed cases. MMRM model will include baseline MAS-B ankle score with knee extended as a covariate and factors of age group, treatment group, visit, treatment-by-visit interaction, study center and previous botulinum toxin exposure. The frequency distribution of the CGI scores, as well as the percentage of responders (CGI score  $\geq 1$ ), will be summarized by treatment group at each post-treatment visit. A logistic regression analysis will also be performed on the responder status at each post-treatment visit with factors of age group, treatment group, study center, and previous botulinum toxin exposure, if applicable.

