### Global Attainment Scale by Physician

Each of the 2 goals for each patient at each visit will be analyzed by an ANCOVA model with age group, treatment group, study center and previous botulinum toxin exposure as factors and baseline MAS-B ankle score with knee extended as a covariate to assess treatment differences. The frequency distribution of raw scores for each goal will be summarized by treatment group. Additionally, the percentages of responders who scored 0 or higher (meet or exceed expectation) and the responders who scored -1 or high (slight improvement but not meet expectation) on each functional goal will also be summarized and responder status will be analyzed by logistic regression with factors of age group, treatment group, study center and previous botulinum toxin exposure, if applicable.

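### The supportive MAS-B, CGI and GAS responder models enter pooled study centre as an ordinary logistic factor, which biases the treatment odds ratios modestly away from 1; conditional logistic regression would remove this

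*SAP*

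**What the plan says.** Three responder outcomes are analysed by logistic regression at each relevant visit.

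- **MAS-B** (SAP 5.2.2; Protocol 7.3.1): response is a fall of one grade or more. The terms are baseline MAS-B "and factors of age group, treatment group, study center, and previous botulinum toxin exposure, if applicable".
- **CGI** (SAP 5.3.1; Protocol 7.3.2): response is a score of +1 or better, analysed "with factors of age group, treatment group, study center, and previous botulinum toxin exposure, if applicable".
- **GAS** (SAP 5.3.2 only; Protocol 7.3.2 gives only ANCOVA for GAS): two thresholds for each of two goals, where "responder status will be analyzed by logistic regression with factors of age group, treatment group, study center and previous botulinum toxin exposure, if applicable".

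The pooling rule is in SAP 2.3. It covers these models because its scope is "For the primary and secondary efficacy analyses where study center is a factor in the analysis model, centers that recruited only a few patients". Centres are ranked by patients enrolled. "Any center with at least 12 patients will stand on its own", and smaller ones are combined within country until they reach 12. SAP 5.2.1 repeats the floor: "Pooled study center will be produced to ensure each contains at least 12 patients".

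The visible text names no conditional, exact, penalised or random-centre method for the responder models. Nor does it say what to do if a centre has all responders or none. The phrase at the end of each model statement, allowing terms where applicable, is not defined. The number of centres is not given.

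**The concern.** In a linear model, extra centre terms cost degrees of freedom but do not bias the treatment effect. In ordinary (unconditional) logistic regression they do. Each centre adds a parameter estimated from only that centre's patients, so the number of parameters grows with the sample and the treatment log odds ratio is pushed away from zero. If BOTOX works, the error is always in its favour.

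The responder odds ratios restate fractional grade differences in terms of patients who improve. MAS-B has 5 visits, CGI has 5, and GAS has 2 goals x 2 thresholds x 2 visits = 8. That makes 18 models and 36 dose-versus-placebo odds ratios. What is at stake is a modest, one-directional overstatement in those supportive figures, together with an unplanned choice for the analyst if a fit gives warnings.

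**Working it through.** **Inputs from the documents.** Pooling floor 12 (SAP 2.3, 5.2.1). Size: "Approximately 412 patients will be enrolled to ensure that at least 351 patients (117 per treatment group) will complete the study" (Protocol 7.5). Table 4: MAS-B change -0.8 v -0.45, SD 0.75; CGI 1.2 v 0.6, SD 1.2. Two-sided 0.05.

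**Assumptions, not in the documents.** Centre sizes, variation between centres, covariate effects, and responder rates derived from Table 4 by normality.

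**1. The plan's own figure.** The documents give no figure for the responder odds ratios, so the check is on the power that uses the same inputs. MAS-B: SE = 0.75 x √(2/117) = 0.098, and 0.35/0.098 = 3.57. CGI: SE = 1.2 x √(2/117) = 0.157, and 0.6/0.157 = 3.82. By the t-test, power is 94.5% and 96.8%; the product is 91.4%. The stated 94%, 97% and 91% reproduce.

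**2. Implied responder rates.** Both scales move in whole grades, so I cut at half a grade.
- MAS-B: placebo Φ((-0.5 + 0.45)/0.75) = 47%; 8 U/kg Φ((-0.5 + 0.8)/0.75) = 66%; odds ratio about 2.1.
- CGI: placebo Φ((0.6 - 0.5)/1.2) = 53%; 8 U/kg Φ((1.2 - 0.5)/1.2) = 72%; odds ratio about 2.25.
- Cutting at a full grade lowers the rates (MAS-B 23% v 39%, CGI 37% v 57%) but leaves the odds ratios at about 2.2.

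**3. Largest possible number of pooled centres.** 412/12 = 34.

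**4. Approximate bias.** With m patients per centre, the log odds ratio is inflated by about m/(m - 1), so the odds ratio is multiplied by OR^(1/(m - 1)).

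| Patients per centre | log OR factor | OR factor at 2.1 to 2.25 |
|---|---|---|
| 12 | 12/11 = 1.091 | 1.070 to 1.077 |
| 20 | 20/19 = 1.053 | 1.040 to 1.044 |
| 30 | 30/29 = 1.034 | 1.026 to 1.028 |

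**5. Simulation of the specified model.** Runs used about 350-412 patients, three arms and between-centre SD from 0 to 1 on the logit scale.
- 12 per centre: log OR inflated about 9-13%. On the OR scale, exp(0.09 x ln 2.1) = 1.07 and exp(0.13 x ln 2.25) = 1.11.
- 20 per centre: simulated about 6-8%. With the approximation in step 4, the range is about 5-8%.
- 30 per centre: about 2-5%.
- Null rejection at 12 per centre: 5.9-6.6%, 6.0-6.7% and 6.9% in three sets of runs; a fourth with no missing data gave 5.0%. At 20 or more per centre: 5.3-6.0%.

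**6. Effect of dropout.** The floor counts enrolled patients, but the models use observed cases. 12 x 351/412 = 10.2, so a centre at the floor averages about 10 patients by week 12. Simulating 34 such centres with 14.8% missing at random, OR 2.25 and centre SD 0.6 gave a log OR 12.3% too large (2.25 reported as 2.49) and null rejection of 6.6%.

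**7. The alternative on the same data.** With 12 per centre, conditional logistic regression gave 0.97-0.99 of the true log OR, against 1.06-1.08 for the ordinary fit in those 104 and 144 trials (Monte Carlo SE about 0.03-0.04 as a ratio). The ordinary fit was therefore about 9-10% above the conditional one. A Firth-penalised fit gave 0.96-0.98.

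**8. Centres with all or no responders.** With 34 centres of 12 and a common rate p, the chance of at least one is 1 - (1 - p^12 - (1 - p)^12)^34: 2% at p = 50%, 7% at 60%, 38% at 30%, 91% at 80%. With centre SD of 1 it was 63-87% in simulation. Removing such centres changed the treatment log OR by less than 1e-8.

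**The case against.** The best counter-argument is that pooled centres will rarely sit at the floor. Larger centres stand alone at any size, pools may exceed 12, and a short last pool is merged upward. Applying the rule to 412 patients, assuming 30 to 80 sites in 4 countries with a site-size CV of 0.7 to 1.0, gave on average 17 to 26 pooled centres of about 16 to 24 patients. By m/(m - 1), that is 4-7% on the log OR, or about 3-5% on an OR of 2.15. This stands: the 12-per-centre figures describe the unfavourable end, not the expected case.

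It also stands that nothing decisive depends on these models. The gatekeeping (SAP 5.2.1) and Hochberg (SAP 10.1) tests use the MMRM of the continuous scores, and the responder percentages by arm are reported separately and do not involve centre terms.

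A reader might infer more than the documents support:
- **That the plan overstates the odds ratios by some fixed amount, such as 11%.** Centre numbers are not stated, and the inflation depends on them and on the true effect.
- **That separation damages the treatment estimate.** An all-or-none centre makes its own coefficient infinite and may trigger a convergence warning, but the treatment odds ratio does not move.
- **That responder rates are high enough to make such centres likely.** The half-grade rates from Table 4 are mid-range; the chance depends mainly on assumed variation between centres.
- **That the floor of 12 was chosen for the linear models.** Neither document says why it was chosen.

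What survives is that the bias of the stated method runs in one direction, has a known cause, and can be avoided without new data.

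**Conclusion.** The point holds as a limited one. The three responder analyses, as specified, bias the treatment log odds ratio away from the null: by about 9-13% if nearly all pooled centres hold 12 patients, about 5-8% at 20 and about 2-5% at 30. In the first case the odds ratio is about 7-11% too high at the effects implied by Table 4. Null rejection is about 6-7% at 12 per centre in most runs and close to 5% with larger centres, so the bias in the estimate is firmer evidence than the type I error. All these sizes rest on assumed centre sizes and on normality for the responder rates. The primary and co-primary conclusions are not touched. Priority: consider.

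**What to change.** In SAP 5.2.2, 5.3.1 and 5.3.2, fit the responder models by conditional logistic regression stratified by pooled study centre, keep the other listed terms, and drop centre as an explicit factor. Align Protocol 7.3.1 (MAS-B) and 7.3.2 (CGI), or declare the change in SAP section 12, which at present records no deviations from Amendment 3.

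The cost is this wording, a small change in code, and the loss of centre-specific predicted probabilities. No data are needed. Centres with all or no responders drop out of the conditional fit, but they already add nothing to the treatment estimate in the present model.
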